8.2.2 Visit 2 (Baseline + 4 weeks)

For PS0014 study assessments, refer to [Table 5-4](#). In addition, perform the following DV0002 substudy assessments:

- IRT contact
- Blood sample for bimekizumab plasma concentrations (DV0002-specific)—only done for subjects who receive bimekizumab Q4W
- Bimekizumab administration by study personnel using the PFS—only done for subjects who receive bimekizumab Q4W.
- Drug and device accountability (DV0002-specific)—only done for subjects who receive bimekizumab Q4W.

8.2.3 Visit 3 (Baseline + 8 weeks)

For PS0014 study assessments, refer to [Table 5-4](#). In addition, perform the following DV0002 substudy assessments:

- IRT contact.

- Blood sample for bimekizumab plasma concentrations (DV0002-specific).
- Subject self-injection of bimekizumab using the assigned device (DV0002-specific).
- Study personnel evaluation of self-injection (DV0002-specific).
- Complete the VAS for injection site pain (DV0002-specific).
- Complete the post-injection SIAQ Questionnaire (version 2.0 for bimekizumab-SS-2mL and version 2.1 for bimekizumab-AI-2mL) (DV0002-specific).
- Study personnel evaluation of device for structural/mechanical integrity (DV0002-specific).
- Drug and device accountability (DV0002-specific).

8.2.4 Visit 3a (Baseline + 9 weeks; safety follow-up telephone call)

Visit 3a (Week 9) will occur in the DV0002 substudy but not in the PS0014 study. The following procedures/assessments will be performed:

- Concomitant medications.
- Adverse events.

8.2.5 Visit 4 (Baseline + 12 weeks)

For PS0014 study assessments, refer to [Table 5-4](#). In addition, perform the following DV0002 substudy assessments:

- IRT contact.
- Blood sample for bimekizumab plasma concentrations (DV0002-specific)—only done for subjects who receive bimekizumab Q4W.
- Bimekizumab administration by study personnel using the PFS—only done for subjects who receive bimekizumab Q4W.
- Drug and device accountability (DV0002-specific).

8.2.6 Visit 5 (Baseline + 16 weeks)

For PS0014 study assessments, refer to [Table 5-4](#). In addition, perform the following DV0002 substudy assessments:

- IRT contact.
- Blood sample for bimekizumab plasma concentrations (DV0002-specific)—only done for subjects who receive bimekizumab Q8W.
- Bimekizumab administration by study personnel using the PFS. (If this visit coincides with Week 48 of PS0014, subjects will have the option to self-inject; refer to the PS0014 protocol.)
- Drug and device accountability (DV0002-specific).

9 ASSESSMENT OF SELF-INJECTION

Evaluation of dose delivery and safe self-injection will be performed as described for the primary outcome variable (Section 4.1.1).

9.1 Assessment of self-injection experience by SIAQ

The SIAQ will be used to assess the subject's self-injection experience.

The SIAQ was developed by UCB to assess the perceived advantages and the potential limitations of self-injection of an sc medication (Keininger and Coteur, 2011). The pre-injection SIAQ is composed of 7 items grouped into 3 domains (feelings about injection, self-confidence, and satisfaction with the current mode of administration). The post-injection SIAQ is composed of 21 items grouped into 6 domains (feelings about injection, self-image, self-confidence, injection site reactions, ease of use, and satisfaction with self-injection). The pre-injection SIAQ will be completed at Visit 1, and the post-injection SIAQ will be completed within 30 minutes after self-injection (ie, at Visit 1 and Visit 3). For the 1mL device cohort, the SIAQ will be completed within 30 minutes of completing the second injection. For the 2mL device cohort, the SIAQ will be completed within 30 minutes of completing the single injection.

Version 2.0 and version 2.1 of the SIAQ are identical, except for Question 11. In version 2.0 of the SIAQ, Question 11 discusses the use of a plunger, while in version 2.1 of the SIAQ, Question 11 discusses depression of the device. Version 2.0 will therefore be used to assess bimekizumab-SS-1mL and bimekizumab-SS-2mL, while version 2.1 will be used to assess bimekizumab-AI-1mL and bimekizumab-AI-2mL.

9.2 Assessment of injection site pain

A VAS will be used to assess overall injection pain due to self-injection at DV0002 Baseline and at 8 weeks after training. Subjects will be required to indicate their injection pain by placing a mark on a 100mm line from 0 (no pain) to 100 (worst possible pain).

1mL Device Cohort

In the 1mL device cohort of the DV0002 substudy, the 320mg bimekizumab dose will be administered as two 160mg sc injections with either 2 bimekizumab-SS-1mL or 2 bimekizumab-AI-1mL devices. To evaluate injection pain for both self-injections, the VAS will be assessed immediately (within 15 minutes) after completion of the second self-injection. The subject will complete the VAS prior to completion of the post-injection SIAQ (refer to Section 9.1 for details).

2mL Device Cohort

In the 2mL device cohort, the 320mg bimekizumab dose will be administered as 1 sc injection with either the bimekizumab-SS-2mL or bimekizumab-AI-2mL device. To evaluate injection pain for the self-injection, the VAS will be assessed immediately (within 15 minutes) after completion of the self-injection. The subject will complete the VAS prior to completion of the post-injection SIAQ (refer to Section 9.1 for details).

9.3 Evaluation of post-use structural and mechanical integrity of self-injection investigational devices

The visual inspection of the used devices will check for structural/mechanical integrity and damage (ie, clear evidence of damage/compromised structural integrity and not any superficial, cosmetic imperfections). All evaluations will be performed by appropriately trained site staff. Any device with structural/mechanical integrity issues will be returned to UCB for further evaluation. Superficial, cosmetic imperfections which have no impact on structural or mechanical integrity are to be ignored.

Used devices that functioned as intended and which had no post-use structural or mechanical integrity issues (as determined by the post-use site evaluation) will also be returned to UCB for further evaluation.

10 ASSESSMENT OF PHARMACOKINETIC VARIABLES

1mL Device Cohort

Blood samples for measurement of trough bimekizumab PK (Section 4.1.3.2) will be collected at the time points specified in the schedule of study assessments (Table 5-3).

At dosing visits, blood samples will be drawn prior to dosing (at the same time of the sampling for clinical laboratory tests). The time and date of collection will be recorded in the eCRF.

Instructions pertaining to sample collection, processing, storage, labeling, and shipping are provided in the laboratory manual for this study. Detailed information on sample analysis will be provided in a bioanalytical report.

2mL Device Cohort

For subjects who participate in the 2mL device cohort, blood samples for measurement of trough bimekizumab PK levels (Section 4.1.3.2) will be collected at the timepoints specified in Table 10-1.

Table 10-1: DV0002 substudy 2mL device cohort PK sample collection time points

| Dose Regimen | PS0014 Week that subject starts DV0002 | DV0002 Visits | | | | |
|--------------|--|----------------------------|-----------------|-----------------|------------------|------------------|
| | | Visit 1 (Baseline)/ Week 0 | Visit 2/ Week 4 | Visit 3/ Week 8 | Visit 4/ Week 12 | Visit 5/ Week 16 |
| 320mg Q4W | Week 24 | X ^a | X | X | X | X ^a |
| | Week 28 | X | X | X | X ^a | NA |
| | Week 32 | X | X | X ^a | X | X ^a |
| 320mg Q8W | Week 24 | X ^a | NA | X | NA | X ^a |
| | Week 32 | X | NA | X ^a | NA | X ^a |

NA=not applicable; PK=pharmacokinetics; Q4W=every 4 weeks; Q8W=every 8 weeks

Note: For the 2mL device cohort, the DV0002 Baseline visit will be PS0014 Week 24, Week 28, or Week 32 for subjects receiving bimekizumab 320mg Q4W or PS0014 Week 24 or Week 32 for subjects receiving bimekizumab 320mg Q8W.

^a PK sample taken per the PS0014 schedule.

At dosing visits, blood samples will be drawn prior to dosing (at the same time of the sampling for clinical laboratory tests). The time and date of collection will be recorded in the eCRF.

Instructions pertaining to sample collection, processing, storage, labeling, and shipping are provided in the laboratory manual for this study. Detailed information on sample analysis will be provided in a bioanalytical report.

11 ASSESSMENT OF SAFETY

11.1 Adverse events (investigational device)

All AEs (including serious adverse events [SAEs]) will be reported in a common database for PS0014 and DV0002, but only ADEs, SADEs, and device deficiencies will be summarized in the DV0002 substudy. Specifically, only those AEs related to the use of the investigational medical devices (based on the Investigator's judgement) will be assessed. All AEs (including SAEs) which are not assessed to be related to the investigational devices will be summarized separately in the report for the main study, PS0014; please refer to the PS0014 protocol for information on reporting and recording AEs (including SAEs).

11.1.1 Definitions (investigational device)

11.1.1.1 Adverse device effect (investigational device)

An ADE is an AE related to the use of an investigational device. An ADE must meet 1 or more of the following criteria:

- Adverse event resulting from insufficiencies or inadequacies in the IFU, the deployment, the implantation, the installation, the operation, or any malfunction of the investigational medical device.

- Adverse event that is a result of a use error or intentional misuse of the investigational device.

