13.4 Termination of the study

UCB reserves the right to temporarily suspend or prematurely discontinue this study either at a single site, multiple sites, or at all sites at any time for reasons including, but not limited to, safety or ethical issues, inaccurate or incomplete data recording, noncompliance, or unsatisfactory enrollment with respect to quality or quantity.

The study may also be temporarily suspended or prematurely terminated in either of the following situations:

- Severe or serious injection site reaction (eg, bleeding, bruising, pain) that, in the opinion of the Investigator, the overseeing IRB, or the Sponsor, is likely to be seen in other enrolled subjects who have not yet been injected with bimekizumab.
- Unexpected device malfunction leading to a failed or incomplete injection, or resulting in an SAE that, in the opinion of the Investigator, the overseeing IRB, or the Sponsor, is likely to be seen in other enrolled subjects who have not yet been injected with bimekizumab.

If the study is prematurely terminated or suspended, UCB (or designee) will inform the Investigator/institutions and the regulatory authority(ies) of the termination or suspension and the reason(s) for the termination or suspension, in accordance with applicable regulatory requirement(s). The IRB should also be informed and provided with reason(s) for the termination or suspension by the Sponsor or by the Investigator/institution, as specified by the applicable regulatory requirement(s). In addition, arrangements will be made for the return of all unused IMP and other material in accordance with UCB procedures for the study.

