### **2.2.3.3 Safety variable**

The other safety variable is the occurrence of ADEs. An ADE is an adverse event (AE) related to the use of an investigational device. An ADE must meet 1 or more of the following criteria:

- Adverse event resulting from insufficiencies or inadequacies in the instructions for use (IFU), the deployment, the implantation, the installation, the operation, or any malfunction of the investigational medical device.
- Adverse event that is a result of a use error or intentional misuse of the investigational device.

Additional safety and tolerability variables will be collected as described in the PS0014 study protocol.

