### 10.2 Adverse events

All AEs (including serious adverse events [SAEs]) will be reported in a common database for PS0014 and DV0002, but only adverse device effects (ADEs), serious adverse device effects (SADEs), and device deficiencies will be summarized in the DV0002 substudy. Specifically, only those AEs related to the use of the investigational medical devices bimekizumab-SS-

1mL, bimekizumab-AI-1mL, bimekizumab-SS-2 mL or bimekizumab-AI-2 mL (based on the Investigator's judgement) will be assessed. All AEs (including SAEs) which are not assessed to be related to the investigational devices will be summarized separately in the report for the main study PS0014. An exception are AEs that are indicated as injection site reactions during self-injection. These will be listed in DV0002 as well as in PS0014.

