### 10.2.1 Adverse device effects

Adverse events are recorded at the AE CRF page at the time when they occur. If an adverse event is related to the device by assessment of the investigator it is counted as an Adverse device event. For DV0002 only ADE will be considered which started during the DV0002 study period. And ADEs started in the 1 ml phase will be included for 1 ml phase analysis, and those started in the 2 ml phase will be included for the 2 ml phase analysis. For 2 ml phase analysis, adverse device effects include those that started on or before the later of the final contact date or (the last injection date + 7 days).

All ADE data will be listed and no statistical testing will be performed. Only treatment-emergent ADEs will be included in the summary tables. Treatment-emergent ADEs (TEADEs) will be defined as events that have a start date on or following the first self-administration of study treatment in DV0002 through the final self-administration of study treatment + 7 days. The device SFU will occur 1 week after the last self-administration.

All ADEs will be coded and classified by system organ class, high level term, and preferred term. Adverse device effects will be summarized by the frequency and percentage of subjects having 1 or more of the events in question. Additional planned summaries include overall ADEs and SADEs. All summaries are presented by PS0014 treatment

- Incidence of TEADEs – Overview
- Incidence of TEADEs by SOC, HLT, and PT
- Incidence of serious TEADEs by SOC, HLT, and PT
- Incidence of TEADEs leading to death
- Incidence of TEADEs leading to discontinuation
- Incidence of non-TEADEs (only listed and not summarized in a table)

For definition of serious, unanticipated and serious unanticipated ADEs see protocol of DV0002.

Adverse device effects which started before DV0002 Week 16 and were ongoing at the data cut off will be included with the status remaining as ongoing. Adverse device effects which were ongoing at DV0002 Week 16 but with an end date before the data cut off will be included with their end date as recorded.

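### The mandatory criteria in the ADE definition are narrower than the Investigator-relatedness rule used for counting, so harm from correct use of a sound device can be scored either way

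*Protocol*

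**What the plan says.** Protocol 11.1.1.1 gives the definition in two steps: "An ADE is an AE related to the use of an investigational device. An ADE must meet 1 or more of the following criteria". The first criterion is "Adverse event resulting from insufficiencies or inadequacies in the IFU, the deployment, the implantation, the installation, the operation, or any malfunction" of the device. The second is "Adverse event that is a result of a use error or intentional misuse of the investigational device". SAP 2.2.3.3 carries the same two steps, including "An ADE must meet 1 or more of the following criteria".

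Protocol 11.1.1.2 defines a SADE as an ADE with a serious outcome, so SADEs inherit the definition. The safety half of the primary endpoint (Protocol 4.1.1, SAP 2.2.1) requires no SADE and no ADE leading to withdrawal from DV0002. The secondary endpoint uses the same definition at Baseline.

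The rules for what is assessed and counted are worded differently:

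- Protocol 11.1 assesses AEs that the Investigator judges related to device use, and Protocol 11.1.2.1 has the eCRF record whether an AE is device-related.
- SAP 10.2.1 says: "If an adverse event is related to the device by assessment of the investigator it is counted as an Adverse device event".
- SAP 11.1 counts a subject as safe and effective when the CRF answers are yes for complete dose and no for any AE related to use of the device.

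None of these counting rules mentions the two criteria, and neither document says which test takes precedence.

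**The concern.** In the first criterion, deployment and operation are governed by the opening words about insufficiencies or inadequacies. An AE caused by a device that worked as designed and was used as instructed, such as marked bruising or pain from needle insertion or injection speed, satisfies the opening sentence of the definition but, on a literal reading, neither criterion. Such events are foreseeable: Protocol 13.4 gives bleeding, bruising and pain as examples of injection site reactions that, if severe or serious, could lead to suspension of the study.

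ADEs supply the safety half of the primary and secondary endpoints and are the only safety variable specific to DV0002. The SAP counts what the site enters, and Protocol 11.1.1.1 is where the protocol tells the site what an ADE is. An Investigator who follows the opening sentence marks the event; one who follows the *must* may not. With up to 80 sites (Protocol 5.1.2), the same event could be classified in two ways, and the analysis could not recover the difference from the relatedness entry.

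**Working it through.** The plan states no figure for this point, so there is nothing to reproduce. The check sets the rules side by side and then sizes one classification decision.

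**Step 1: one event under each rule.** Take an AE caused by a functioning device used as instructed, with the full dose delivered.

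| Place | Test applied | Does the event count? |
|---|---|---|
| Protocol 11.1.1.1 and SAP 2.2.3.3, opening sentence | Related to device use | Yes |
| Same sections, mandatory criteria | Inadequacy, malfunction, use error or misuse | No, read literally |
| Protocol 4.1.1 and SAP 2.2.1, safety criterion | SADE, or ADE leading to withdrawal | Only if it is an ADE and is serious or leads to withdrawal |
| Protocol 11.1 and 11.1.2.1 | Investigator's judgement, recorded in the eCRF | Yes, if marked |
| SAP 10.2.1 | Investigator's assessment | Yes, if marked; tabulated if it starts from the first self-injection to the last + 7 days |
| SAP 11.1, counting rule | Any device-related AE on the CRF page | Yes, if marked, whether or not serious |

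Two mismatches appear. The mandatory criteria are narrower than the relatedness test. Separately, the SAP 11.1 counting rule (any device-related AE) is wider than the endpoint criterion it implements (SADEs, or ADEs leading to withdrawal).

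**Step 2: what follows if the Investigator applies the *must*.** The answer to the CRF question can be no, and SAP 11.1 then counts the subject as a success. The AE goes to the PS0014 report (Protocol 11.1). If it is an injection site reaction in the self-injection window, it is also listed in DV0002 (SAP 10.2 and 10.2.2), but a listing neither changes the endpoint nor adds to the ADE tables.

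**Step 3: size per subject.** Inputs: about 100 subjects per 1mL arm and about 50 per 2mL arm (Protocol 5.1.2); 90% exact binomial CI (Protocol 14.2 and 14.3.1). Assumptions: every planned subject is observed at the scored visit, all other subjects succeed, and the event occurs at that visit.

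- Change in the estimate per subject: 1/100 = 1 point; 1/50 = 2 points.
- With x successes out of n, the lower limit is the 5% quantile of Beta(x, n-x+1) and the upper limit is the 95% quantile of Beta(x+1, n-x). When x = n, the lower limit is 0.05^(1/n) and the upper limit is 100%.

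| n per arm | Subjects reclassified (assumed) | Estimate | 90% CI |
|---|---|---|---|
| 100 | 0 | 100% | 97.0-100 |
| 100 | 1 | 99% | 95.3-99.9 |
| 100 | 2 | 98% | 93.8-99.6 |
| 50 | 0 | 100% | 94.2-100 |
| 50 | 1 | 98% | 90.9-99.9 |
| 50 | 2 | 96% | 87.9-99.3 |

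The first reclassified subject lowers the lower limit by 97.0 - 95.3 = 1.7 points at n=100 and by 94.2 - 90.9 = 3.3 points at n=50.

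**The case against.** The strongest reply is that the criteria never enter the calculation. SAP 10.2.1 and 11.1 work from Investigator-assessed relatedness, with no cause criterion, and the SAP 11.1 rule is stricter than the protocol because any device-related AE fails the subject. A reader might infer from the *must* wording that harm from correct use can never fail the primary endpoint or appear in the ADE tables. The documents do not support that: once the Investigator marks the event device-related, it does fail the endpoint and, if treatment-emergent, is tabulated. This part of the reply stands.

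A reader might also infer, from "An exception are AEs that are indicated as injection site reactions during self-injection" in SAP 10.2, that the sponsor expected these reactions to fall outside device-related events. SAP 10.2 gives no reason for the exception. It shows only that such reactions are listed whether or not they are attributed to the device.

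Further points carry some weight. Pain is also captured by the VAS, and injection site reactions by an SIAQ domain. An Investigator could reasonably read bruising as an inadequacy in deployment or operation, and the eCRF completion guidelines, which are not among the documents, may settle the matter. The suspension trigger in Protocol 13.4 does not depend on the ADE definition. Under SAP 3.1, outcome percentages use only subjects with observed data, so someone who stops before Week 8 is absent from the Week 8 percentage and is not a success there. The shifts shown above therefore apply only to events at the visit being scored.

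This does not remove the conflict. Every counting rule rests on the Investigator's answer, and the definition given to the Investigator can lead to the opposite answer for the same event.

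**Conclusion.** The concern holds as an inconsistency of definition. The opening sentence, the mandatory criteria, the relatedness rule and the endpoint safety criterion do not describe the same set of events. The exposure is conditional: a subject harmed by correct use of a sound device is scored as a safe self-injection only if the dose was complete and the Investigator, applying the *must*, did not mark the event device-related.

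Each such subject is worth 1 point in a 1mL arm or 2 points in a 2mL arm. How many there would be cannot be derived from the documents; the counts used here are assumptions, as is full observation at the planned arm sizes. The study is descriptive, with no hypothesis test and no success threshold, so no decision rule is affected. What is affected is the meaning of the reported success and ADE percentages, which are the study's main results.

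**What to change.** 1. In Protocol 11.1.1.1 and SAP 2.2.3.3, replace "An ADE must meet 1 or more of the following criteria" with inclusive wording such as *ADEs include, but are not limited to*.
2. In the same places, state that Investigator-assessed relatedness to device use governs, and that this covers events arising when a functioning device is used as instructed.
3. Reconcile the endpoint safety criterion in Protocol 4.1.1 and SAP 2.2.1 (SADEs, or ADEs leading to withdrawal) with the counting rule in SAP 11.1 (any device-related AE), so that the stated endpoint and the programmed endpoint are the same.
4. Tell sites of the clarified definition, and check that the eCRF completion guidelines agree with it.

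The cost is wording changes in both documents and a note to sites. The downside is that ADE incidence may be slightly higher.
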